In case of DGF, treatment will be according to local practice, but the randomized study regimen cannot be interrupted for more than 21 consecutive days. DGF treatments must maintain sufficient immunological coverage for the graft and may include maintaining, interrupting or reducing the dose of CNI and the use of anti-thymocyte globulin. In case of use of depleting antibody hematological parameters (e.g. lymphocytes, WBC and platelets) must be monitored carefully. Use of MPA and everolimus in subjects randomized to the other treatment arm (i.e. everolimus or MPA respectively) is prohibited during any interruption whether for DGF or other reasons

If a subject with DGF is not able to return to or maintain their randomized study regimen as per protocol after 21 consecutive days of interruption, the subject should be discontinued from the study. If a subject is placed on permanent dialysis (or retransplanted) the Graft Loss, and Adverse Event CRFs should be completed, as well as an SAE report of Graft Loss submitted. Dialysis treatments should be recorded on the Dialysis CRF. Retransplantation should be recorded on the surgical and medical procedures CRF.

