5.5.12 Early study termination

The study can be terminated at any time for any reason by Novartis. Should this be necessary, the subject should be seen as soon as possible and treated as for a prematurely withdrawn subject. The investigator may be informed of additional procedures to be followed in order to ensure that adequate consideration is given to the protection of the subject's interests. The investigator will be responsible for informing IRBs and/or ECs of the early termination of the trial.

6 Visit schedule and assessments

Table 6-1 lists all of the assessments and indicates with an "X" when the visits are to be performed. "A" indicates assessments only to be performed for subjects maintaining the study regimen (i.e. EVR+CNI or MPA+CNI). Subjects should be seen for all visits on the designated day or as close to it as possible.

The day of randomization will be considered to be study Day 1. Subjects will make scheduled study visits on Day 4, at the end of Weeks 1, 2 and 4 at the end of Months 2, 4, 6, 9, 12, 18 and 24. All randomized subjects are expected to continue in the study up to Month 24 regardless of being on or off randomized treatment status. Subjects who discontinue their randomized study treatment regimen should be treated according to standard of care immunosuppression and return for the assessments indicated by X in Table 6-1. If they refuse to return for these assessments or are unable to do so, every effort should be made to contact them or a knowledgeable informant by telephone to determine the subject and graft status.

At a minimum, subjects will be contacted for safety evaluations (SAEs) during the 30 days following the last study visit. Documentation of attempts to contact the subject should be recorded in the source documentation.

Assessment schedule- Study Treatment to Month 24 Table 6-1

Study Period	Screening ¹		Treatment to Month 12									Extension Treatment to Month 24		
Visit	SCR	BL ²	D4	W1	W2	W4	M2	M4	М6	М9	M12	M18	M2 4	
Visit Number	1	99	101	102	103	104	105	106	107	108	199	201	299	
Informed Consent ¹	Х													
Demographics	Х													
Inclusion/	X	Х												
Exclusion														
Medical History	Х												 	
Kidney Transplant Background Recipient/Donor		X												
Kidney Transplant Procedure		Х												
Viral serology ³ Recipient/Donor		Х												
Pregnancy test ⁴	Х								Х		Х	Х	Х	
IRT call	S	S												
Screening Disposition ¹		Х												

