- 7. Central laboratory tests at each visit indicated include: **Biochemistry** (sodium, potassium, chloride, calcium, Cystatin C, magnesium, inorganic phosphate, urea, creatinine, uric acid, AST, ALT, alkaline phosphatase, total bilirubin, CPK, lipase and amylase); Hematology (platelets, hemoglobin, red blood cell (RBC), white blood cell (WBC) and differential count): Lipids: total cholesterol, HDL, LDL and triglycerides Urinalysis (protein, creatinine, albumin, glucose; proteinuria and albuminuria per 24hr period will be estimated from spot protein/creatinine and albumin/creatinine ratios). For subjects who have discontinued study regimen who continue in the study to Month 24 all central laboratory assessments, including serum creatinine for renal function, should be performed, where no central laboratory serum creatinine is available local laboratory serum creatinine should be obtained. HbA1c and fasting plasma glucose will also be carried out by the central laboratory at Week 4 and Months 4, 6, 9, 12 18 and 24. At certain centers, in agreement with the sponsor, central analysis of everolimus levels may be performed.
- 8. Induction therapy (basiliximab or rATG) should be recorded on the Concomitant Medications CRF under the Immunosuppressive Medications category. Pre-transplant CNI or MPA, if used, should be also recorded on the Concomitant medication CRF under the immunosuppressive category.
- All serious adverse events, serious infections and pregnancies must be reported from informed consent until 30 days after the last study visit post randomization (i.e. to the Month 12/24 visit or early discontinuation from study).
- 10. All subjects are expected to continue in the study to Month 24 regardless of whether they are on or off randomized study regimen, if subjects discontinue randomized study regimen they should continue on standard of care and attend study visits to M24. Any permanent discontinuation of the randomized study regimen should be recorded on the appropriate DAR(s) (everolimus MPA, tacrolimus or cyclosporine as needed). Post discontinuation of study regimen the immunosuppressive

Amended Protocol Version v01 Clean

Study Period	Screen	ning¹	Treatm	ent to	Month	12						Extens Treatn to Mor	nent
Visit	SCR	BL ²	D4	W1	W2	W4	M2	M4	М6	М9	M12	M18	M2 4
Visit Number	1	99	101	102	103	104	105	106	107	108	199	201	299

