6.4 Efficacy

Treated Biopsy Proven Acute Rejection (tBPAR)

A treated BPAR is any condition where the subject received anti-rejection treatment and was histologically diagnosed as acute rejection (according to the Banff 2009 criteria, Appendix 6). Renal biopsies will be collected for all cases of suspected acute rejection.

Kidney allograft biopsy

For all suspected rejection episodes, regardless of initiation of anti-rejection treatment, an allograft biopsy must be performed within 48 hrs. Biopsies will be read by the local pathologist according to the updated Banff 2009 criteria (Appendix 6). The results of the biopsy read by the local pathologist will be listed on the Kidney Allograft Biopsy CRF. The results will be used for subject management for acute rejection. The local pathologist will remain blinded to

treatment. Any biopsies performed according to local practice (e.g. not for cause) should also be recorded.

Graft Loss

The allograft will be presumed to be lost on the day the subject starts dialysis and is not able to subsequently be removed from dialysis. If the subject undergoes allograft nephrectomy prior to starting permanent dialysis, then the day of nephrectomy is the day of graft loss. The reason for graft loss will be recorded on the Graft Loss CRF. This will be reported on the M12 or M24 study completion CRF with Graft Loss as the reason for study discontinuation and on the appropriate Dosage Administration Record CRF(s) if death occurs while on randomized treatment. Graft loss is considered a Serious Adverse Event and should be reported on the Adverse Event CRF (as serious) and the SAE reported to the local Novartis Drug Safety and Epidemiology Department local Novartis Drug Safety and Epidemiology (DS&E) Department within 24 hr.

Death

In the event of subject death, the SAE leading to Death should be reported to Novartis DS&E within 24 hr. The events leading to the death should be entered on the Adverse Event CRF and the death should be indicated on the appropriate Dosage Administration Record CRF(s) (if death occurs while on randomized treatment) and on the Study Completion CRF.

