9.4.3 Handling of missing values/censoring/discontinuations

Since the subjects who have prematurely discontinued study regimen are followed on standard of care, renal function data (e.g. creatinine) and kidney allograft biopsy data will be collected post discontinuation of study regimen for these visits, it is expected that few subjects would be missing efficacy and/or renal function evaluation for the 12 month analysis.

To define the primary variable – composite endpoint of tBPAR or eGFR (MDRD4) < 50 mL/min/1.73m², the following imputation method will be applied for subjects with missing 12month eGFR value. As allograft biopsy data will be collected on an as needed basis due to the nature of kidney transplant studies, no particular rule for missing biopsy will be applied.

- Under the assumption of missing not at random (MNAR), subjects who lost their grafts will be assigned a value of zero for their 12-month eGFR;
- Otherwise, under the assumption of missing at random (MAR), subjects who had missing values including those who died with a functioning graft will have a 12-month eGFR imputed using multiple imputation method based on the longitudinal eGFR (MDRD4) data at all available time points and covariates of randomization strata (donor type and CNI), HLA mismatches ($\leq 3 \text{ vs} > 3$) and induction.

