## 4.2 Missing Data Handling

### 4.2.1 Missing GFR Data Imputation

#### 4.2.1.1 Main Imputation

The following is the main imputation method for handling missing eGFR data at Month 12. A similar imputation rule can be applied for missing eGFR at Month 24. These imputations will be applied to the primary analyses for the composite endpoint of tBPAR or eGFR < 50 mL/min/1.73m^2, as well as for eGFR alone. For the component of eGFR < 50 mL/min/1.73m^2, a value for missing eGFR as a continuous variable will be imputed first, then it will be dichotomized in order to derive this endpoint.

- Under the assumption of missing not at random (MNAR), patients who lost their grafts will be assigned a value of zero for their missing eGFR at the visits on and after graft loss;
- Multiple imputation: Otherwise, under the assumption of missing at random (MAR), patients who had missing values including those who died with a functioning graft will have a 12-month eGFR imputed using multiple imputation method based on the covariates/factors CNI, region, donor type, HLA mismatch ( $\leq 3$  vs  $> 3$ ), induction therapy, recipient gender, recipient age, donor age, and DGF, and all eGFR (MDRD4) data collected at the visit windows during the analysis period of interest. In the multiple imputation, recipient age, donor age and eGFR (MDRD4) data will be treated as continuous variables. To help preserve the relationship between outcome and covariates within each treatment, a separate model will be run for each treatment. This will also help ensure that the imputation model does not make stronger assumptions on data relations than the analysis model.

To ensure that results can be replicated, the data should be sorted by patient number before running the model (the data should be in horizontal format with one row per patient). If there are multiple renal function assessments within a visit window, guidelines given in [Section 2.1](#) will be followed, i.e., the closest value to the planned visit (midpoint of visit window for post-baseline visits) will be taken (if tie, the last will be used) for imputation. In addition, the seed used in the multiple imputation will be 2433.

See dummy SAS codes below.

```
proc mi data=DATAIN out=DATAOUT nimpute=100 seed=2433;
  by treatment;
  class CNI region donor HLA induction gender_r DGF;
```

```
fcs reg (/details);  
var CNI region donor HLA induction gender_r age_r age_d DGF GFR_vis1  
GFR_VIS2 ... GFR_VISm;  
run;

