#### 4.2.1.2 Imputation for Sensitivity Analyses

For sensitivity analyses for the composite endpoint of tBPAR or eGFR < 50 mL/min/1.73m^2 as well as for eGFR alone, the following imputation method will be used to impute missing eGFR values at Month 12. Similar imputation rules can be applied to missing GFR at Month 24. Patients who lost their grafts will be assigned a value of zero for their missing eGFR at the visits on and after graft loss. Otherwise, patient who had missing value including those who died with a functioning graft will have a 12-month eGFR imputed using the control-based imputation under the assumption of missing not at random (MNAR). Missing eGFR values in EVR + rCNI arm will be imputed based on the data from the control arm (MPA + sCNI) as everolimus patients would switch to control (standard care) or control-like medication after they discontinue everolimus.

The imputation will be based on CNI, region, donor type, HLA mismatch ( $\leq 3$  vs  $> 3$ ), induction therapy, recipient gender, recipient age, donor age, DGF, and eGFR (MDRD4) at Week 4 as covariates/factors, and all eGFR (MDRD4) data collected at the visit windows during the analysis period of interest. In the multiple imputation, recipient age, donor age and eGFR (MDRD4) data will be treated as continuous variables.

See dummy SAS codes as below:

```
proc mi data= seed=2433 nimpute=100 out=mi_out;  
class treatment CNI region donor HLA induction gender_r DGF;  
fcs reg (/details);  
mnar model (GFR_VIS1 GFR_VIS2 ... GFR_VISm / modelobs = (treatment="MPA"));  
var CNI region donor HLA induction gender_r age_r age_d DGF GFR_VIS1  
GFR_VIS2 ... GFR_VISm;  
run;
```

To ensure that results can be replicated, the data should be sorted by patient number before running the model (the data should be in horizontal format with one row per patient). patientIf there are multiple renal function assessments within a visit window, guidelines given in [Section 2.1](#) will be followed. In addition, the seed used in the multiple imputation will be 2433.

[figure not shown]

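### eGFR is set to zero after graft loss only where it is missing, so a recorded value from a second kidney could be scored as study-graft function; exposure and effect are small

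*SAP*

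**What the plan says.** The primary endpoint (SAP 2.5.1) is tBPAR or eGFR (MDRD4) below 50 at Month 12. Graft loss is not a component, so a lost graft without tBPAR becomes a failure only through its eGFR value.

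- **Zero rule.** Under SAP 4.2.1.1, patients who lost their grafts are "assigned a value of zero for their missing eGFR at the visits on and after graft loss". SAP 4.2.1.2 has the same limit: "Patients who lost their grafts will be assigned a value of zero for their missing eGFR at the visits on and after graft loss". In Protocol 9.4.3 the graft-loss bullet sits under a lead-in with the same effect: "the following imputation method will be applied for subjects with missing 12month eGFR value".
- **Data used.** SAP 2.1 bases the renal analyses primarily on all available data, including data after study medication stops. SAP 4.1 places unscheduled assessments in the visit windows.
- **Follow-up after graft loss.** Protocol 6.4 reports graft loss on the completion form "with Graft Loss as the reason for study discontinuation", and Protocol 5.5.9 lists it among the reasons for leaving the study. Protocol Section 6, however, states: "All randomized subjects are expected to continue in the study up to Month 24 regardless of being on or off randomized treatment status". For subjects off regimen who continue to Month 24, footnote 7 of Protocol Table 6-1 says "all central laboratory assessments, including serum creatinine for renal function, should be performed".
- **Retransplantation.** Protocol 5.5.5 foresees it: "Retransplantation should be recorded on the surgical and medical procedures CRF". Neither document says how eGFR is handled afterwards.
- **Cut-off.** SAP 2.1 ends the 12-month data two weeks after the disposition date, and no later than Day 450. The 24-month analysis has no cut-off day.

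**The concern.** The plan treats a lost graft as having no function, but it does so only where no creatinine happens to have been recorded. Where one exists, it stands as the function of the study graft.

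After retransplantation that value belongs to another kidney. If it is 50 or more and the patient had no tBPAR, a lost graft is scored as no event on the primary composite. On dialysis the MDRD4 value does not measure graft function, so a patient contributes zero or a positive number to the eGFR ANCOVA depending on whether a sample was drawn. The mixed model for slope (SAP 2.7.3.2) uses no imputation and would take any recorded post-loss value as it stands. In an open-label trial, a fixed rule is better than one that depends on whether a sample was drawn.

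**Working it through.** **1. The plan's own figure, for scale.** Protocol Table 9-1 gives non-inferiority power above 99% with 1020 per arm, a 50% event rate, a 10-point margin and one-sided alpha of 0.025.

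- Standard error = sqrt(2 × 0.25 / 1020) = 0.0221.
- Power = Φ(0.10 / 0.0221 − 1.96) = 99.5%, so the figure is reproduced.
- The 95% CI half-width is 1.96 × 0.0221 = 4.34 points. One reclassified patient moves an arm's rate by 1/1020 = 0.098 points.

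**2. Can a dialysis creatinine score as a success?** SAP 4.5.1 gives eGFR = 186.3 × C^−1.154 × A^−0.203 × G × R. The creatinine levels below are illustrative assumptions, for a non-black man aged 50:

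| Creatinine (mg/dL) | eGFR |
|---|---|
| 4 | 17.0 |
| 6 | 10.6 |
| 8 | 7.6 |

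All are below 50. Solving for eGFR = 50 gives C = 1.57 mg/dL for this man. Over ages 20 to 70, both sexes and both race factors, the range is 1.14 to 2.18. A value from dialysis at the levels shown therefore remains an event. A functioning second kidney can reach 50.

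**3. Who is exposed at Month 12?** The Month 12 window is Days 316 to 450 (SAP Table 4-1), and 12-month data stop at disposition + 14 days. Since 316 − 14 = 302, a patient discontinued at graft loss before about Day 302 has no value in the window and receives zero as intended. The exposed groups are:

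- patients kept in the study after graft loss, on which Protocol Section 6 and Protocol 6.4 pull in different directions;
- losses from about Day 302 onward;
- the Month 24 analysis, which has no cut-off.

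A related gap: if a graft is lost inside the window and the selected value was taken before the loss, eGFR is not missing. With a value of 50 or more, that patient also scores as no event.

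**4. Size on the binary endpoint.** The documents give no graft-loss or retransplantation rates. Assume 2% to 5% graft loss by Month 12, 5% to 20% of those retransplanted with a Month 12 creatinine, and half of these at 50 or above:

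- Low: 0.02 × 0.05 × 0.5 = 0.05 points (about 0.5 patients of 1020).
- High: 0.05 × 0.20 × 0.5 = 0.5 points (about 5 patients of 1020).

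These figures do not allow for step 3, and they do not remove patients who already fail through tBPAR.

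**5. Size on mean eGFR.** Assume 3% graft loss, half of these with a dialysis creatinine of 4 to 8 mg/dL. The arm mean shifts by 0.03 × 0.5 × 7.6 = 0.11 to 0.03 × 0.5 × 17.0 = 0.26 mL/min/1.73m².

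**The case against.** The strongest reply is that the data flow already closes most of the gap. Graft loss ends study participation under Protocol 6.4, and footnote 7 of Table 6-1 asks for creatinine only from off-regimen subjects who continue in the study. For a late loss handled under Protocol 6.4, a false success through a second kidney would need retransplantation and recovery to 50 within about 14 days. This stands and greatly narrows Month 12 exposure. It does not cover patients retained under the Section 6 instruction, or Month 24.

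A second reply is the worst-value rule in SAP 2.1 for events defined on a quantitative measure: one low value in the window would make the patient an event. This helps only in part. SAP 4.2.1.1 takes the value closest to the window midpoint for imputation, so the two rules need reconciling. Neither helps if every value in the window comes from a functioning second kidney.

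Third, graft loss is counted directly in the key secondary endpoint, which gates superiority, and in the composite of tBPAR, graft loss, death or eGFR below 50. That is correct and limits the consequence, but it does not repair the primary variable.

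A reader might infer that dialysis values also turn lost grafts into successes, or that lost grafts in general escape the primary endpoint. The documents support neither: step 2 rules out the first at the creatinine levels shown, and the discontinuation rule with the cut-off contradicts the second.

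**Conclusion.** The point holds in a narrow form. Both SAP imputation sections limit the zero to missing values, and nothing overrides a recorded post-loss value. In the exposed cases, the binary endpoint can be wrong through a second kidney or a pre-loss value inside the Month 12 window. The continuous MDRD4 analyses can take a positive dialysis value where the plan intends zero.

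The effect is small. Under the assumed rates, the second-kidney route hides at most about 0.5 points of failures per arm before allowing for the cut-off, against a CI half-width of 4.34 points and a margin of 10. The arm mean of eGFR moves by about 0.1 to 0.3 mL/min/1.73m². Only a between-arm imbalance biases the treatment difference. Sample size and design power are unchanged. This is a clarification worth making, not a threat to the primary conclusion.

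**What to change.** Change the SAP only:

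1. In 4.2.1.1 and 4.2.1.2, set eGFR to zero at every visit on or after the graft-loss date, regardless of any recorded creatinine, for both Month 12 and Month 24.
2. Score a graft lost within the Month 12 analysis window (Days 316 to 450, up to the cut-off) as zero at Month 12, even if the selected value precedes the loss.

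Protocol 9.4.3 should be left alone. Its graft-loss bullet does not contain the limiting word, and removing that word from the lead-in would blur which subjects are imputed at all. The cost is a small SAP revision and a short change to the derivation code, with no new data.

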#### 4.2.1.2 Imputation for Sensitivity Analyses

For sensitivity analyses for the composite endpoint of tBPAR or eGFR < 50 mL/min/1.73m^2 as well as for eGFR alone, the following imputation method will be used to impute missing eGFR values at Month 12. Similar imputation rules can be applied to missing GFR at Month 24. Patients who lost their grafts will be assigned a value of zero for their missing eGFR at the visits on and after graft loss. Otherwise, patient who had missing value including those who died with a functioning graft will have a 12-month eGFR imputed using the control-based imputation under the assumption of missing not at random (MNAR). Missing eGFR values in EVR + rCNI arm will be imputed based on the data from the control arm (MPA + sCNI) as everolimus patients would switch to control (standard care) or control-like medication after they discontinue everolimus.

The imputation will be based on CNI, region, donor type, HLA mismatch ( $\leq 3$  vs  $> 3$ ), induction therapy, recipient gender, recipient age, donor age, DGF, and eGFR (MDRD4) at Week 4 as covariates/factors, and all eGFR (MDRD4) data collected at the visit windows during the analysis period of interest. In the multiple imputation, recipient age, donor age and eGFR (MDRD4) data will be treated as continuous variables.

See dummy SAS codes as below:

```
proc mi data= seed=2433 nimpute=100 out=mi_out;  
class treatment CNI region donor HLA induction gender_r DGF;  
fcs reg (/details);  
mnar model (GFR_VIS1 GFR_VIS2 ... GFR_VISm / modelobs = (treatment="MPA"));  
var CNI region donor HLA induction gender_r age_r age_d DGF GFR_VIS1  
GFR_VIS2 ... GFR_VISm;  
run;
```

To ensure that results can be replicated, the data should be sorted by patient number before running the model (the data should be in horizontal format with one row per patient). patientIf there are multiple renal function assessments within a visit window, guidelines given in [Section 2.1](#) will be followed. In addition, the seed used in the multiple imputation will be 2433.

[figure not shown]
